3 – Severe	xx (xx.x%)	xx (xx.x%)
Week 2		
n	xx	xx
0 – None	xx (xx.x%)	xx (xx.x%)
1 – Mild	xx (xx.x%)	xx (xx.x%)
2 – Moderate	xx (xx.x%)	xx (xx.x%)
3 – Severe	xx (xx.x%)	xx (xx.x%)
Week 4		
n	xx	xx
0 – None	xx (xx.x%)	xx (xx.x%)
1 – Mild	xx (xx.x%)	xx (xx.x%)
2 – Moderate	xx (xx.x%)	xx (xx.x%)
3 – Severe	xx (xx.x%)	xx (xx.x%)

Note: No imputation of missing data.

SOURCE: USERNAME\SPONSOR\PROJECT\JOBNAME (DATE,TIME)

Table 14.3.1.1: Summary of Cutaneous Signs and Local Tolerability at Each Evaluation
(Safety Population)
(Page 6 of 14)

Pigmentation	E-BPO/E-ATRA 3%/0.1% Cream (N=xxx)	Vehicle Cream (N=xxx)
Week 8		
n	xx	xx
0 – None	xx (xx.x%)	xx (xx.x%)
1 – Mild	xx (xx.x%)	xx (xx.x%)
2 – Moderate	xx (xx.x%)	xx (xx.x%)
3 – Severe	xx (xx.x%)	xx (xx.x%)
Week 12		
n	xx	xx
0 – None	xx (xx.x%)	xx (xx.x%)
1 – Mild	xx (xx.x%)	xx (xx.x%)
2 – Moderate	xx (xx.x%)	xx (xx.x%)
3 – Severe	xx (xx.x%)	xx (xx.x%)

Note: No imputation of missing data.

SOURCE: USERNAME\SPONSOR\PROJECT\JOBNAME (DATE,TIME)

Table 14.3.1.1: Summary of Cutaneous Signs and Local Tolerability at Each Evaluation
(Safety Population)
(Page 7 of 14)

Dryness	E-BPO/E-ATRA 3%/0.1% Cream (N=xxx)	Vehicle Cream (N=xxx)
Baseline		
n	xx	xx
0 – None	xx (xx.x%)	xx (xx.x%)
1 – Mild	xx (xx.x%)	xx (xx.x%)
2 – Moderate	xx (xx.x%)	xx (xx.x%)
3 – Severe	xx (xx.x%)	xx (xx.x%)
Week 2		
n	xx	xx
0 – None	xx (xx.x%)	xx (xx.x%)
1 – Mild	xx (xx.x%)	xx (xx.x%)
2 – Moderate	xx (xx.x%)	xx (xx.x%)
3 – Severe	xx (xx.x%)	xx (xx.x%)
Week 4		
n	xx	xx
0 – None	xx (xx.x%)	xx (xx.x%)
1 – Mild	xx (xx.x%)	xx (xx.x%)
2 – Moderate	xx (xx.x%)	xx (xx.x%)
3 – Severe	xx (xx.x%)	xx (xx.x%)

Note: No imputation of missing data.

SOURCE: USERNAME\SPONSOR\PROJECT\JOBNAME (DATE,TIME)

Table 14.3.1.1: Summary of Cutaneous Signs and Local Tolerability at Each Evaluation
(Safety Population)
(Page 8 of 14)

Dryness	E-BPO/E-ATRA 3%/0.1% Cream (N=xxx)	Vehicle Cream (N=xxx)
Week 8		
n	xx	xx
0 – None	xx (xx.x%)	xx (xx.x%)
1 – Mild	xx (xx.x%)	xx (xx.x%)
2 – Moderate	xx (xx.x%)	xx (xx.x%)
3 – Severe	xx (xx.x%)	xx (xx.x%)
Week 12		
n	xx	xx
0 – None	xx (xx.x%)	xx (xx.x%)
1 – Mild	xx (xx.x%)	xx (xx.x%)
2 – Moderate	xx (xx.x%)	xx (xx.x%)
3 – Severe	xx (xx.x%)	xx (xx.x%)

Note: No imputation of missing data.

SOURCE: USERNAME\SPONSOR\PROJECT\JOBNAME (DATE,TIME)

Table 14.3.1.1: Summary of Cutaneous Signs and Local Tolerability at Each Evaluation
(Safety Population)
(Page 9 of 14)

Itching	E-BPO/E-ATRA 3%/0.1% Cream (N=xxx)	Vehicle Cream (N=xxx)
Baseline		
n	xx	xx
0 – None	xx (xx.x%)	xx (xx.x%)
1 – Mild	xx (xx.x%)	xx (xx.x%)
2 – Moderate	xx (xx.x%)	xx (xx.x%)
3 – Severe	xx (xx.x%)	xx (xx.x%)
Week 2		
n	xx	xx
0 – None	xx (xx.x%)	xx (xx.x%)
1 – Mild	xx (xx.x%)	xx (xx.x%)
2 – Moderate	xx (xx.x%)	xx (xx.x%)
3 – Severe	xx (xx.x%)	xx (xx.x%)
Week 4		
n	xx	xx
0 – None	xx (xx.x%)	xx (xx.x%)
1 – Mild	xx (xx.x%)	xx (xx.x%)
2 – Moderate	xx (xx.x%)	xx (xx.x%)
3 – Severe	xx (xx.x%)	xx (xx.x%)

Note: No imputation of missing data.

SOURCE: USERNAME\SPONSOR\PROJECT\JOBNAME (DATE,TIME)

Table 14.3.1.1: Summary of Cutaneous Signs and Local Tolerability at Each Evaluation
(Safety Population)
(Page 10 of 14)

Itching	E-BPO/E-ATRA 3%/0.1% Cream (N=xxx)	Vehicle Cream (N=xxx)
Week 8		
n	xx	xx
0 – None	xx (xx.x%)	xx (xx.x%)
1 – Mild	xx (xx.x%)	xx (xx.x%)
2 – Moderate	xx (xx.x%)	xx (xx.x%)
3 – Severe	xx (xx.x%)	xx (xx.x%)
Week 12		
n	xx	xx
0 – None	xx (xx.x%)	xx (xx.x%)
1 – Mild	xx (xx.x%)	xx (xx.x%)
2 – Moderate	xx (xx.x%)	xx (xx.x%)
3 – Severe	xx (xx.x%)	xx (xx.x%)

Note: No imputation of missing data.

SOURCE: USERNAME\SPONSOR\PROJECT\JOBNAME (DATE,TIME)

Table 14.3.1.1: Summary of Cutaneous Signs and Local Tolerability at Each Evaluation
(Safety Population)
(Page 11 of 14)

Burning	E-BPO/E-ATRA 3%/0.1% Cream (N=xxx)	Vehicle Cream (N=xxx)
Baseline		
n	xx	xx
0 – None	xx (xx.x%)	xx (xx.x%)
1 – Mild	xx (xx.x%)	xx (xx.x%)
2 – Moderate	xx (xx.x%)	xx (xx.x%)
3 – Severe	xx (xx.x%)	xx (xx.x%)
Week 2		
n	xx	xx
0 – None	xx (xx.x%)	xx (xx.x%)
1 – Mild	xx (xx.x%)	xx (xx.x%)
2 – Moderate	xx (xx.x%)	xx (xx.x%)
3 – Severe	xx (xx.x%)	xx (xx.x%)
Week 4		
n	xx	xx
0 – None	xx (xx.x%)	xx (xx.x%)
1 – Mild	xx (xx.x%)	xx (xx.x%)
2 – Moderate	xx (xx.x%)	xx (xx.x%)
3 – Severe	xx (xx.x%)	xx (xx.x%)

Note: No imputation of missing data.

SOURCE: USERNAME\SPONSOR\PROJECT\JOBNAME (DATE,TIME)

Table 14.3.1.1: Summary of Cutaneous Signs and Local Tolerability at Each Evaluation
(Safety Population)
(Page 12 of 14)

Burning	E-BPO/E-ATRA 3%/0.1% Cream (N=xxx)	Vehicle Cream (N=xxx)
Week 8		
n	xx	xx
0 – None	xx (xx.x%)	xx (xx.x%)
1 – Mild	xx (xx.x%)	xx (xx.x%)
2 – Moderate	xx (xx.x%)	xx (xx.x%)
3 – Severe	xx (xx.x%)	xx (xx.x%)
Week 12		
n	xx	xx
0 – None	xx (xx.x%)	xx (xx.x%)
1 – Mild	xx (xx.x%)	xx (xx.x%)
2 – Moderate	xx (xx.x%)	xx (xx.x%)
3 – Severe	xx (xx.x%)	xx (xx.x%)

Note: No imputation of missing data.

SOURCE: USERNAME\SPONSOR\PROJECT\JOBNAME (DATE,TIME)

Table 14.3.1.1: Summary of Cutaneous Signs and Local Tolerability at Each Evaluation
(Safety Population)
(Page 13 of 14)

Stinging	E-BPO/E-ATRA 3%/0.1% Cream (N=xxx)	Vehicle Cream (N=xxx)
Baseline		
n	xx	xx
0 – None	xx (xx.x%)	xx (xx.x%)
1 – Mild	xx (xx.x%)	xx (xx.x%)
2 – Moderate	xx (xx.x%)	xx (xx.x%)
3 – Severe	xx (xx.x%)	xx (xx.x%)
Week 2		
n	xx	xx
0 – None	xx (xx.x%)	xx (xx.x%)
1 – Mild	xx (xx.x%)	xx (xx.x%)
2 – Moderate	xx (xx.x%)	xx (xx.x%)
3 – Severe	xx (xx.x%)	xx (xx.x%)
Week 4		
n	xx	xx
0 – None	xx (xx.x%)	xx (xx.x%)
1 – Mild	xx (xx.x%)	xx (xx.x%)
2 – Moderate	xx (xx.x%)	xx (xx.x%)
3 – Severe	xx (xx.x%)	xx (xx.x%)

Note: No imputation of missing data.

SOURCE: USERNAME\SPONSOR\PROJECT\JOBNAME (DATE,TIME)

Table 14.3.1.1: Summary of Cutaneous Signs and Local Tolerability at Each Evaluation
(Safety Population)
(Page 14 of 14)

Stinging	E-BPO/E-ATRA 3%/0.1% Cream (N=xxx)	Vehicle Cream (N=xxx)
Week 8		
n	xx	xx
0 – None	xx (xx.x%)	xx (xx.x%)
1 – Mild	xx (xx.x%)	xx (xx.x%)
2 – Moderate	xx (xx.x%)	xx (xx.x%)
3 – Severe	xx (xx.x%)	xx (xx.x%)
Week 12		
n	xx	xx
0 – None	xx (xx.x%)	xx (xx.x%)
1 – Mild	xx (xx.x%)	xx (xx.x%)
2 – Moderate	xx (xx.x%)	xx (xx.x%)
3 – Severe	xx (xx.x%)	xx (xx.x%)

Note: No imputation of missing data.

SOURCE: USERNAME\SPONSOR\PROJECT\JOBNAME (DATE,TIME)

Table 14.3.1.2.1: Summary of Treatment-Emergent Adverse Event Characteristics
(Safety Population)
(Page 1 of 2)

	E-BPO/E-ATRA 3%/0.1% Cream (N=xxx)	Vehicle Cream (N=xxx)
Subjects Reporting Any Treatment-Emergent Adverse Event	xx (xx.x%)	xx (xx.x%)
Number of Treatment-Emergent Adverse Events	xx	xx
Subjects Reporting Any Serious Treatment-Emergent Adverse Event	xx (xx.x%)	xx (xx.x%)
Number of Serious Treatment-Emergent Adverse Events	xx	xx
Subjects Reporting Treatment-Emergent Adverse Event with Outcome of Fatal	xx (xx.x%)	xx (xx.x%)
Number of Treatment-Emergent Adverse Events with Outcome of Fatal	xx	xx
Subjects Who Discontinued Study Drug Due to a Treatment-Emergent Adverse Event	xx (xx.x%)	xx (xx.x%)
Number of Treatment-Emergent Adverse Events Leading to Discontinuation of Study Drug	xx	xx
Subjects Who Discontinued from the Study Due to a Treatment-Emergent Adverse Event	xx (xx.x%)	xx (xx.x%)
Number of Treatment-Emergent Adverse Events Leading to Discontinuation of Study	xx	xx

Note: Treatment-emergent adverse events are those events that were not indicated as occurring prior to first application.
Related defined as “Definitely”, “Probably”, or “Possible”. Not Related defined as “Unlikely” or “Not related”.

SOURCE: USERNAME\SPONSOR\PROJECT\JOBNAME (DATE, TIME)

Table 14.3.1.2.1: Summary of Treatment-Emergent Adverse Event Characteristics
(Safety Population)
(Page 2 of 2)

	E-BPO/E-ATRA 3%/0.1% Cream (N=xxx)	Vehicle Cream (N=xxx)
By Maximum Severity		
Severe	xx (xx.x%)	xx (xx.x%)
Moderate	xx (xx.x%)	xx (xx.x%)
Mild	xx (xx.x%)	xx (xx.x%)
By Strongest Relationship to Study Drug		
Related	xx (xx.x%)	xx (xx.x%)
Not Related	xx (xx.x%)	xx (xx.x%)
Maximum Severity within Relationship to Study Drug		
Related		
Severe	xx (xx.x%)	xx (xx.x%)
Moderate	xx (xx.x%)	xx (xx.x%)
Mild	xx (xx.x%)	xx (xx.x%)
Not Related		
Severe	xx (xx.x%)	xx (xx.x%)
Moderate	xx (xx.x%)	xx (xx.x%)
Mild	xx (xx.x%)	xx (xx.x%)

Note: Treatment-emergent adverse events are those events that were not indicated as occurring prior to first application.
Related defined as “Definitely”, “Probably”, or “Possible”. Not Related defined as “Unlikely” or “Not related”.

SOURCE: USERNAME/SPONSOR/PROJECT/JOBNAME (DATE, TIME)

Table 14.3.1.2.2: Summary of Treatment-Emergent Adverse Events by MedDRA System Organ Class and Preferred Term
(Safety Population)
(Page 1 of x)

System Organ Class ^a Preferred Term	E-BPO/E-ATRA 3%/0.1% Cream (N=xxx)	Vehicle Cream (N=xxx)	P-Value ^b
XXXXXXXXXXXXXXXXXXXXXXXXXXXX	xx (xx.x%)	xx (xx.x%)	x.xxx
XXXXXXXXXXXXXXXXXXXXXXXXXXXX	xx (xx.x%)	xx (xx.x%)	x.xxx

^a Counts reflect numbers of subjects reporting one or more adverse events that map to MedDRA. At each level of summarization (System Organ Class or Preferred Term) subjects are counted once.

^b P-value for the difference between treatment groups from a Fisher’s Exact test. The specific system organ classes and preferred terms analyzed will be those that are reported by at least one percent of the patients in any treatment group.

Note: MedDRA Version 21.0

Treatment-emergent adverse events are those events that were not indicated as occurring prior to first application.

SOURCE: USERNAME\SPONSOR\PROJECT\JOBNAME (DATE, TIME)

Table 14.3.1.2.3: Summary of Treatment-Emergent Adverse Events by Severity
(Safety Population)
(Page 1 of x)

System Organ Class ^a Preferred Term	Severity	E-BPO/E-ATRA 3%/0.1% Cream (N=xxx)	Vehicle Cream (N=xxx)
XXXXXXXXXXXXXXXXXXXXXXXXXXXX	Severe	xx (xx.x%)	xx (xx.x%)
	Moderate	xx (xx.x%)	xx (xx.x%)
	Mild	xx (xx.x%)	xx (xx.x%)
XXXXXXXXXXXXXXXXXXXXXXXXXXXX	Severe	xx (xx.x%)	xx (xx.x%)
	Moderate	xx (xx.x%)	xx (xx.x%)
	Mild	xx (xx.x%)	xx (xx.x%)

^a Counts reflect numbers of subjects reporting one or more adverse events that map to MedDRA. At each level of summarization (System Organ Class or Preferred Term) subjects are counted once under the greatest reported severity.

Note: MedDRA Version 21.0.

Treatment-emergent adverse events are those events that were not indicated as occurring prior to first application.

SOURCE: USERNAME\SPONSOR\PROJECT\JOBNAME (DATE, TIME)

Table 14.3.1.2.4: Summary of Treatment-Emergent Adverse Events by Relationship to Study Drug
(Safety Population)
(Page 1 of xx)

System Organ Class ^a Preferred Term	Relationship	E-BPO/E-ATRA 3%/0.1% Cream (N=xxx)	Vehicle Cream (N=xxx)
xxxxxxxxxxxxxxxxxxxxxxxxxxxxxxxx	Related	xx (xx.x%)	xx (xx.x%)
	Not Related	xx (xx.x%)	xx (xx.x%)
xxxxxxxxxxxxxxxxxxxxxxxxxxxxxxxx	Related	xx (xx.x%)	xx (xx.x%)
	Not Related	xx (xx.x%)	xx (xx.x%)

^a Counts reflect numbers of subjects reporting one or more adverse events that map to MedDRA. At each level of summarization (System Organ Class or Preferred Term) subjects are counted once under the greatest reported relationship.

Note: MedDRA Version 21.0.

Treatment-emergent adverse events are those events that were not indicated as occurring prior to first application.

Related defined as “Definitely”, “Probably”, or “Possible”. Not Related defined as “Unlikely” or “Not related”.

SOURCE: USERNAME\SPONSOR\PROJECT\JOBNAME (DATE, TIME)

Table 14.3.1.3.1: Summary of Treatment-Emergent Serious Adverse Event Characteristics
(Safety Population)
(Page 1 of 2)

	E-BPO/E-ATRA 3%/0.1% Cream (N=xxx)	Vehicle Cream (N=xxx)
Subjects Reporting Any Serious Treatment-Emergent Adverse Event	xx (xx.x%)	xx (xx.x%)
Number of Serious Treatment-Emergent Adverse Events	xx	xx
Subjects Reporting Serious Treatment-Emergent Adverse Event with Outcome of Fatal	xx (xx.x%)	xx (xx.x%)
Number of Serious Treatment-Emergent Adverse Events with Outcome of Fatal	xx	xx
Subjects Who Discontinued Study Drug Due to a Serious Treatment-Emergent Adverse Event	xx (xx.x%)	xx (xx.x%)
Number of Serious Treatment-Emergent Adverse Events Leading to Discontinuation of Study Drug	xx	xx
Subjects Who Discontinued from the Study Due to a Serious Treatment-Emergent Adverse Event	xx (xx.x%)	xx (xx.x%)
Number of Serious Treatment-Emergent Adverse Events Leading to Discontinuation of Study	xx	xx

Note: Treatment-emergent adverse events are those events that were not indicated as occurring prior to first application.
Related defined as “Definitely”, “Probably”, or “Possible”. Not Related defined as “Unlikely” or “Not related”.

SOURCE: USERNAME\SPONSOR\PROJECT\JOBNAME (DATE, TIME)

Table 14.3.1.3.1: Summary of Treatment-Emergent Serious Adverse Event Characteristics
(Safety Population)
(Page 2 of 2)

	E-BPO/E-ATRA 3%/0.1% Cream (N=xxx)	Vehicle Cream (N=xxx)
By Maximum Severity		
Severe	xx (xx.x%)	xx (xx.x%)
Moderate	xx (xx.x%)	xx (xx.x%)
Mild	xx (xx.x%)	xx (xx.x%)
By Strongest Relationship to Study Drug		
Related	xx (xx.x%)	xx (xx.x%)
Not Related	xx (xx.x%)	xx (xx.x%)
Maximum Severity within Relationship to Study Drug		
Related		
Severe	xx (xx.x%)	xx (xx.x%)
Moderate	xx (xx.x%)	xx (xx.x%)
Mild	xx (xx.x%)	xx (xx.x%)
Not Related		
Severe	xx (xx.x%)	xx (xx.x%)
Moderate	xx (xx.x%)	xx (xx.x%)
Mild	xx (xx.x%)	xx (xx.x%)

Note: Treatment-emergent adverse events are those events that were not indicated as occurring prior to first application.
Related defined as “Definitely”, “Probably”, or “Possible”. Not Related defined as “Unlikely” or “Not related”.

SOURCE: USERNAME/SPONSOR/PROJECT\JOBNAME (DATE, TIME)

Table 14.3.1.3.2: Summary of Treatment-Emergent Serious Adverse Events by MedDRA System Organ Class and Preferred Term
(Safety Population)
(Page 1 of x)

System Organ Class ^a Preferred Term	E-BPO/E-ATRA 3%/0.1% Cream (N=xxx)	Vehicle Cream (N=xxx)	P-Value ^b
XXXXXXXXXXXXXXXXXXXXXXXXXXXX	xx (xx.x%)	xx (xx.x%)	x.xxx
XXXXXXXXXXXXXXXXXXXXXXXXXXXX	xx (xx.x%)	xx (xx.x%)	x.xxx

^a Counts reflect numbers of subjects reporting one or more adverse events that map to MedDRA. At each level of summarization (System Organ Class or Preferred Term) subjects are counted once.

^b P-value for the difference between treatment groups from a Fisher’s Exact test. The specific system organ classes and preferred terms analyzed will be those that are reported by at least one percent of the patients in any treatment group.

Note: MedDRA Version 21.0

Treatment-emergent adverse events are those events that were not indicated as occurring prior to first application.

SOURCE: USERNAME\SPONSOR\PROJECT\JOBNAME (DATE, TIME)

Table 14.3.1.3.3: Summary of Serious Treatment-Emergent Adverse Events by Severity
(Safety Population)
(Page 1 of x)

System Organ Class ^a Preferred Term	Severity	E-BPO/E-ATRA 3%/0.1% Cream (N=xxx)	Vehicle Cream (N=xxx)
XXXXXXXXXXXXXXXXXXXXXXXXXXXX	Severe	xx (xx.x%)	xx (xx.x%)
	Moderate	xx (xx.x%)	xx (xx.x%)
	Mild	xx (xx.x%)	xx (xx.x%)
XXXXXXXXXXXXXXXXXXXXXXXXXXXX	Severe	xx (xx.x%)	xx (xx.x%)
	Moderate	xx (xx.x%)	xx (xx.x%)
	Mild	xx (xx.x%)	xx (xx.x%)

^a Counts reflect numbers of subjects reporting one or more serious adverse events that map to MedDRA. At each level of summarization (System Organ Class or Preferred Term) subjects are counted once under the greatest reported severity.

Note: MedDRA Version 21.0.

Treatment-emergent adverse events are those events that were not indicated as occurring prior to first application.

SOURCE: USERNAME\SPONSOR\PROJECT\JOBNAME (DATE, TIME)

Table 14.3.1.3.4: Summary of Treatment-Emergent Serious Adverse Events by Relationship to Study Drug
(Safety Population)
(Page 1 of xx)

System Organ Class ^a Preferred Term	Relationship	E-BPO/E-ATRA 3%/0.1% Cream (N=xxx)	Vehicle Cream (N=xxx)
xxxxxxxxxxxxxxxxxxxxxxxxxxxxxxxx	Related	xx (xx.x%)	xx (xx.x%)
	Not Related	xx (xx.x%)	xx (xx.x%)
xxxxxxxxxxxxxxxxxxxxxxxxxxxxxxxx	Related	xx (xx.x%)	xx (xx.x%)
	Not Related	xx (xx.x%)	xx (xx.x%)

^a Counts reflect numbers of subjects reporting one or more serious adverse events that map to MedDRA. At each level of summarization (System Organ Class or Preferred Term) subjects are counted once under the greatest reported relationship.

Note: MedDRA Version 21.0.

Treatment-emergent adverse events are those events that were not indicated as occurring prior to first application.

Related defined as “Definitely”, “Probably”, or “Possible”. Not Related defined as “Unlikely” or “Not related”.

SOURCE: USERNAME\SPONSOR\PROJECT\JOBNAME (DATE, TIME)

Table 14.3.1.4: Summary of Vital Signs
(Safety Population)
(Page 1 of 5)

Temperature (°C)	E-BPO/E-ATRA 3%/0.1% Cream (N=xxx)	Vehicle Cream (N=xxx)
Baseline		
n	xxx	xxx
Mean	xx.x	xx.x
SD	xx.xx	xx.xx
Median	xx.x	xx.x
Min. to Max.	xx to xx	xx to xx
Week 12		
n	xxx	xxx
Mean	xx.x	xx.x
SD	xx.xx	xx.xx
Median	xx.x	xx.x
Min. to Max.	xx to xx	xx to xx
Change from Baseline		
n	xxx	xxx
Mean	xx.x	xx.x
SD	xx.xx	xx.xx
Median	xx.x	xx.x
Min. to Max.	xx to xx	xx to xx

Note: No imputation of missing values. Negative change values represent decrease from Baseline.

SOURCE: USERNAME\SPONSOR\PROJECT\JOBNAME (DATE, TIME)

Table 14.3.1.4: Summary of Vital Signs
(Safety Population)
(Page 2 of 5)

Respiratory Rate (breaths/min)	E-BPO/E-ATRA 3%/0.1% Cream (N=xxx)	Vehicle Cream (N=xxx)
Baseline		
n	xxx	xxx
Mean	xx.x	xx.x
SD	xx.xx	xx.xx
Median	xx.x	xx.x
Min. to Max.	xx to xx	xx to xx
Week 12		
n	xxx	xxx
Mean	xx.x	xx.x
SD	xx.xx	xx.xx
Median	xx.x	xx.x
Min. to Max.	xx to xx	xx to xx
Change from Baseline		
n	xxx	xxx
Mean	xx.x	xx.x
SD	xx.xx	xx.xx
Median	xx.x	xx.x
Min. to Max.	xx to xx	xx to xx

Note: No imputation of missing values. Negative change values represent decrease from Baseline.

SOURCE: USERNAME\SPONSOR\PROJECT\JOBNAME (DATE, TIME)

Table 14.3.1.4: Summary of Vital Signs
(Safety Population)
(Page 3 of 5)

Systolic Blood Pressure (mmHg)	E-BPO/E-ATRA 3%/0.1% Cream (N=xxx)	Vehicle Cream (N=xxx)
Baseline		
n	xxx	xxx
Mean	xx.x	xx.x
SD	xx.xx	xx.xx
Median	xx.x	xx.x
Min. to Max.	xx to xx	xx to xx
Week 12		
n	xxx	xxx
Mean	xx.x	xx.x
SD	xx.xx	xx.xx
Median	xx.x	xx.x
Min. to Max.	xx to xx	xx to xx
Change from Baseline		
n	xxx	xxx
Mean	xx.x	xx.x
SD	xx.xx	xx.xx
Median	xx.x	xx.x
Min. to Max.	xx to xx	xx to xx

Note: No imputation of missing values. Negative change values represent decrease from Baseline.

SOURCE: USERNAME\SPONSOR\PROJECT\JOBNAME (DATE, TIME)

Table 14.3.1.4: Summary of Vital Signs
(Safety Population)
(Page 4 of 5)

Diastolic Blood Pressure (mmHg)	E-BPO/E-ATRA 3%/0.1% Cream (N=xxx)	Vehicle Cream (N=xxx)
Baseline		
n	xxx	xxx
Mean	xx.x	xx.x
SD	xx.xx	xx.xx
Median	xx.x	xx.x
Min. to Max.	xx to xx	xx to xx
Week 12		
n	xxx	xxx
Mean	xx.x	xx.x
SD	xx.xx	xx.xx
Median	xx.x	xx.x
Min. to Max.	xx to xx	xx to xx
Change from Baseline		
n	xxx	xxx
Mean	xx.x	xx.x
SD	xx.xx	xx.xx
Median	xx.x	xx.x
Min. to Max.	xx to xx	xx to xx

Note: No imputation of missing values. Negative change values represent decrease from Baseline.

SOURCE: USERNAME\SPONSOR\PROJECT\JOBNAME (DATE, TIME)

Table 14.3.1.4: Summary of Vital Signs
(Safety Population)
(Page 5 of 5)

Heart Rate (beats/min)	E-BPO/E-ATRA 3%/0.1% Cream (N=xxx)	Vehicle Cream (N=xxx)
Baseline		
n	xxx	xxx
Mean	xx.x	xx.x
SD	xx.xx	xx.xx
Median	xx.x	xx.x
Min. to Max.	xx to xx	xx to xx
Week 12		
n	xxx	xxx
Mean	xx.x	xx.x
SD	xx.xx	xx.xx
Median	xx.x	xx.x
Min. to Max.	xx to xx	xx to xx
Change from Baseline		
n	xxx	xxx
Mean	xx.x	xx.x
SD	xx.xx	xx.xx
Median	xx.x	xx.x
Min. to Max.	xx to xx	xx to xx

Note: No imputation of missing values. Negative change values represent decrease from Baseline.

SOURCE: USERNAME\SPONSOR\PROJECT\JOBNAME (DATE, TIME)

Table 14.3.1.4.2: Shift Table of Vital Signs
(Safety Population)

	E-BPO/E-ATRA 3%/0.1% Cream (N=xxx)			Vehicle Cream (N=xxx)		
Systolic Blood Pressure (mmHg)	Week 12			Week 12		
Baseline	<90 mmHg	90-140 mmHg	>140 mmHg	<90 mmHg	90-140 mmHg	>140 mmHg
<90 mmHg	xx (xx.x%)	xx (xx.x%)	xx (xx.x%)	xx (xx.x%)	xx (xx.x%)	xx (xx.x%)
90-140 mmHg	xx (xx.x%)	xx (xx.x%)	xx (xx.x%)	xx (xx.x%)	xx (xx.x%)	xx (xx.x%)
>140 mmHg	xx (xx.x%)	xx (xx.x%)	xx (xx.x%)	xx (xx.x%)	xx (xx.x%)	xx (xx.x%)
Diastolic Blood Pressure (mmHg)	Week 12			Week 12		
Baseline	<90 mmHg	90-100 mmHg	>100 mmHg	<90 mmHg	90-100 mmHg	>100 mmHg
<90 mmHg	xx (xx.x%)	xx (xx.x%)	xx (xx.x%)	xx (xx.x%)	xx (xx.x%)	xx (xx.x%)
90-100 mmHg	xx (xx.x%)	xx (xx.x%)	xx (xx.x%)	xx (xx.x%)	xx (xx.x%)	xx (xx.x%)
>100 mmHg	xx (xx.x%)	xx (xx.x%)	xx (xx.x%)	xx (xx.x%)	xx (xx.x%)	xx (xx.x%)
Heart Rate (beats/min)	Week 12			Week 12		
Baseline	<60 bpm	60-100 bpm	>100 bpm	<60 bpm	60-100 bpm	>100 bpm
<60 mmHg	xx (xx.x%)	xx (xx.x%)	xx (xx.x%)	xx (xx.x%)	xx (xx.x%)	xx (xx.x%)
60-100 mmHg	xx (xx.x%)	xx (xx.x%)	xx (xx.x%)	xx (xx.x%)	xx (xx.x%)	xx (xx.x%)
>100 mmHg	xx (xx.x%)	xx (xx.x%)	xx (xx.x%)	xx (xx.x%)	xx (xx.x%)	xx (xx.x%)

Note: No imputation of missing values.

SOURCE: USERNAME\SPONSOR\PROJECT\JOBNAME (DATE, TIME)

Table 14.3.1.5: Summary of Abnormal Physical Examination Findings by Visit
(Safety Population)

	E-BPO 3% Cream (N=xxx)	Vehicle Cream (N=xxx)
Heart		
Baseline		
n	xx	xx
Abnormal	xx (xx.x%)	xx (xx.x%)
Week 12		
n	xx	xx
Abnormal	xx (xx.x%)	xx (xx.x%)
Lung		
Baseline		
n	xx	xx
Abnormal	xx (xx.x%)	xx (xx.x%)
Week 12		
n	xx	xx
Abnormal	xx (xx.x%)	xx (xx.x%)
Abdomen		
Baseline		
n	xx	xx
Abnormal	xx (xx.x%)	xx (xx.x%)
Week 12		
n	xx	xx
Abnormal	xx (xx.x%)	xx (xx.x%)

Note: No imputation of missing values.

SOURCE: USERNAME\SPONSOR\PROJECT\JOBNAME (DATE, TIME)

Table 14.3.1.6: Summary of Patient Global Impression of Treatment Side-Effects (PGI-SE) at Each Evaluation
(Safety Population)
(Page 1 of 2)

Right now, how bothered are you by the side effects of your acne treatment:	E-BPO/E-ATRA 3%/0.1% Cream (N=xxx)	Vehicle Cream (N=xxx)
Week 2		
n	xx	xx
0 - I am not bothered	xx (xx.x%)	xx (xx.x%)
1 - I am somewhat bothered	xx (xx.x%)	xx (xx.x%)
2 - I am moderately bothered	xx (xx.x%)	xx (xx.x%)
3 - I am very bothered	xx (xx.x%)	xx (xx.x%)
4 - I am extremely bothered	xx (xx.x%)	xx (xx.x%)
Week 4		
n	xx	xx
0 - I am not bothered	xx (xx.x%)	xx (xx.x%)
1 - I am somewhat bothered	xx (xx.x%)	xx (xx.x%)
2 - I am moderately bothered	xx (xx.x%)	xx (xx.x%)
3 - I am very bothered	xx (xx.x%)	xx (xx.x%)
4 - I am extremely bothered	xx (xx.x%)	xx (xx.x%)
Week 8		
n	xx	xx
0 - I am not bothered	xx (xx.x%)	xx (xx.x%)
1 - I am somewhat bothered	xx (xx.x%)	xx (xx.x%)
2 - I am moderately bothered	xx (xx.x%)	xx (xx.x%)
3 - I am very bothered	xx (xx.x%)	xx (xx.x%)
4 - I am extremely bothered	xx (xx.x%)	xx (xx.x%)

Note: No imputation of missing values.

SOURCE: USERNAME/SPONSOR/PROJECTJOBNAME (DATE,TIME)

Table 14.3.1.6: Summary of Patient Global Impression of Treatment Side-Effects (PGI-SE) at Each Evaluation
(Safety Population)
(Page 2 of 2)

Right now, how bothered are you by the side effects of your acne treatment:	E-BPO/E-ATRA 3%/0.1% Cream (N=xxx)	Vehicle Cream (N=xxx)
Week 12		
n	xx	xx
0 - I am not bothered	xx (xx.x%)	xx (xx.x%)
1 - I am somewhat bothered	xx (xx.x%)	xx (xx.x%)
2 - I am moderately bothered	xx (xx.x%)	xx (xx.x%)
3 - I am very bothered	xx (xx.x%)	xx (xx.x%)
4 - I am extremely bothered	xx (xx.x%)	xx (xx.x%)

[figure not shown]
Note: No imputation of missing values.

SOURCE: USERNAME\SPONSOR\PROJECT\JOBNAME (DATE,TIME)

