12.20 Patient-Reported Outcomes (PRO)

There are five PRO questionnaires to be administered in the study and each is summarized below. Each will be administered to all Patients, from the age of 9 years old, during the designated study visits with instructions from the Study Staff that they be completed:

- Only by the Patient without amendment or interpretation of the Patient's response by a clinician or anyone else.
- Prior to any other assessments or procedures.

In the event the Patient skips any questionnaire item(s); the Study Staff will ask the Patient to complete the form. The PRO questionnaire data will be entered into the eCRF, and a copy will be placed with the Patient source at the site according to the ICH-GCP guideline.

The Patient-Reported Evaluation of Facial Acne (PRE-FACE): The PRE-FACE, which can be completed in less than 2 minutes, is a seven item PRO questionnaire that assesses acne vulgaris-related signs, symptoms and impacts. The four-item acne sign and symptom domain (ASD) assesses the severity of acne vulgaris-related pimples, whiteheads, blackheads, and redness, at their worst, in the 24 hours prior to

administration on an 11-point numeric rating scale (NRS) ranging from 0 (“no [Concept] at all”) to 10 (“[Concept] as bad as you can imagine”). The three-item acne impact domain (AID) assesses acne vulgaris-related embarrassment, self-consciousness, and sadness in the seven days prior to administration on an 11-point NRS ranging from 0 (“not [Concept] at all”) to 10 (“extremely [Concept]”). The PRE-FACE will be administered at study visits 2-6, including Screening, Baseline, and at Weeks 2, 4, 8, and 12/ End of Study or Early Termination.

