1. LIST OF ABBREVIATIONS AND DEFINITIONS OF TERMS

Acne-QoL	Acne Quality-of-Life Questionnaire
AE(s)	adverse event(s)
AID	Acne impact domain
ANCOVA	analysis of covariance
ANOVA	analysis of variance
ATC	Anatomical Therapeutic Chemical
ASD	acne sign and symptom domain
BMI	body mass index
C	Celsius
cm	centimeters
CRF(s)	case report form(s)
eCRF(s)	electronic case report form(s)
E-BPO	encapsulated benzoyl peroxide
FDA	Food and Drug Administration
GCP	good clinical practice
IGA	Investigator Global Assessment
ITT	Intent-to-Treat
IWRS	Interactive Web Response System
kg	kilograms
LOCF	last observation carried forward
LSMean or LSM	least square mean
max	maximum
MCMC	Markov Chain Monte Carlo
MedDRA	Medical Dictionary for Regulatory Activities
mg	milligram
min	minimum
n	number of observations
N	number of subjects (sample size)
PRO	Patient Reported Outcome
PRE-FACE	Patient-Reported Evaluation of Facial Acne
PGI-C	Patient Global Impression of Change

PGI-S	Patient Global Impression of Symptom Severity
PGI-SE	Patient Global Impression of Treatments Side Effects
PGI-TS	Patient Global Impression of Treatments Satisfaction
PP	per-protocol
PT	preferred term
QST	QST Consultations, Ltd.
SAE(s)	serious adverse event(s)
SAS®	Statistical Analysis System (SAS® Institute Inc., Cary, NC)
SD	standard deviation
SOC	system organ class
TEAE(s)	treatment-emergent adverse event(s)
WHO	World Health Organization

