7.1.3 Supportive Efficacy Endpoints

The supportive efficacy endpoints are as follows:

- Proportion of Patients with an assessment of clear or almost clear and with at least a 2-grade improvement in IGA from Baseline, at Weeks 2, 4 and 8.
- Absolute change from Baseline in inflammatory and non-inflammatory lesion counts from Baseline to Week 2.
- PRE-FACE ASD: Mean absolute change in PRE-FACE ASD scores from Baseline to Weeks 2, 4, and 8.
- PRE-FACE AID: Mean absolute change in PRE-FACE AID scores from Baseline to Weeks 2, 4, and 8.
- Proportion of Patients in treatment relative to control who report at least “minimally improved” as measured by the PGI-C at Week 12.
- Patient Global Impress of Symptom Severity (PGI-S) at Week 12.
- Patient Global Impression of Treatment Satisfaction (PGI-TS) at Week 12.

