8.1.4 Adjustments for Covariates

Baseline lesion count will be a covariate for the primary efficacy endpoint for acne lesion counts. No other covariates are planned to be used in the analyses for this study.

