	E-BPO/E-ATRA 3%/0.1% Cream (N=xxx)	Vehicle Cream (N=xxx)	Skewness P-Value	Treatment P-Value
PRE-FACE Item 1 (Pimples) –Absolute Change from Baseline to Week 8 ^d				
LSMean ^a	xx.x	xx.x	x.xxx ^b	x.xxx ^a
LSSD ^a	xx.xx	xx.xx		x.xxx ^c
PRE-FACE Item 2 (Blackheads) –Absolute Change from Baseline to Week 8				
LSMean ^a	xx.x	xx.x	x.xxx ^b	x.xxx ^a
LSSD ^a	xx.xx	xx.xx		x.xxx ^c
PRE-FACE Item 3 (Whiteheads) –Absolute Change from Baseline to Week 8				
LSMean ^a	xx.x	xx.x	x.xxx ^b	x.xxx ^a
LSSD ^a	xx.xx	xx.xx		x.xxx ^c
PRE-FACE Item 4 (Redness) –Absolute Change from Baseline to Week 8				
LSMean ^a	xx.x	xx.x	x.xxx ^b	x.xxx ^a
LSSD ^a	xx.xx	xx.xx		x.xxx ^c

^a Least squares means, standard deviations and treatment p-value from an analysis of covariance with factors of treatment and analysis center and the respective Baseline lesion count as a covariate. Negative least squares means values represent decrease from Baseline.

^b Skewness test, based on methods presented by J.H. Zar (1984), assessed for each imputed dataset.

^c P-value from a ranked analysis of covariance with factors of treatment and analysis center and the respective Baseline lesion count as a covariate.

^d Multiple imputation used to impute missing values for only item 1 (pimples).

SOURCE: USERNAME\SPONSOR\PROJECT\JOBNAME (DATE, TIME)

Table 14.2.12.1: Supportive Efficacy Analyses: PRE-FACE ASD Scores
(Intent-to-Treat Population)
(Page 2 of 3)

	E-BPO/E-ATRA 3%/0.1% Cream (N=xxx)	Vehicle Cream (N=xxx)	Skewness P-Value	Treatment P-Value
PRE-FACE Item 1 (Pimples) –Absolute Change from Baseline to Week 4 ^d				
LSMean ^a	xx.x	xx.x	x.xxx ^b	x.xxx ^a
LSSD ^a	xx.xx	xx.xx		x.xxx ^c
PRE-FACE Item 2 (Blackheads) –Absolute Change from Baseline to Week 4				
LSMean ^a	xx.x	xx.x	x.xxx ^b	x.xxx ^a
LSSD ^a	xx.xx	xx.xx		x.xxx ^c
PRE-FACE Item 3 (Whiteheads) –Absolute Change from Baseline to Week 4				
LSMean ^a	xx.x	xx.x	x.xxx ^b	x.xxx ^a
LSSD ^a	xx.xx	xx.xx		x.xxx ^c
PRE-FACE Item 4 (Redness) –Absolute Change from Baseline to Week 4				
LSMean ^a	xx.x	xx.x	x.xxx ^b	x.xxx ^a
LSSD ^a	xx.xx	xx.xx		x.xxx ^c

^a Least squares means, standard deviations and treatment p-value from an analysis of covariance with factors of treatment and analysis center and the respective Baseline lesion count as a covariate. Negative least squares means values represent decrease from Baseline.

^b Skewness test, based on methods presented by J.H. Zar (1984), assessed for each imputed dataset.

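### The table footnotes for the PRE-FACE item analyses name a baseline lesion count as covariate, which matches no PRE-FACE item, and the SAP does not say whether ASD and AID scores mean items or domains

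*SAP*

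**What the plan says.** SAP 7.1.3 lists two supportive endpoints: "PRE-FACE ASD: Mean absolute change in PRE-FACE ASD scores from Baseline to Weeks 2, 4, and 8" and "PRE-FACE AID: Mean absolute change in PRE-FACE AID scores from Baseline to Weeks 2, 4, and 8". The SAP abbreviation list expands the two terms as "acne sign and symptom domain" and "Acne impact domain". Protocol 12.20 describes their content: "The four-item acne sign and symptom domain (ASD) assesses the severity of acne vulgaris-related pimples, whiteheads, blackheads, and redness", and "The three-item acne impact domain (AID) assesses acne vulgaris-related embarrassment" together with self-consciousness and sadness.

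The results are planned in Table 14.2.12.1 (items 1 to 4) and Table 14.2.13.1 (items 5 to 7), each at Weeks 8, 4 and 2. On every page of both tables, footnote a (parametric) and footnote c (ranked) describe an ANCOVA with "factors of treatment and analysis center and the respective Baseline lesion count as a covariate". Footnote b says that skewness is tested in each imputed dataset. Footnote d says that only item 1 (first table) or item 5 (second table) is imputed.

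SAP 8.1.4 assigns baseline lesion count to the primary lesion count endpoint and then closes the list: "No other covariates are planned to be used in the analyses for this study". SAP 8.7.4 says only that continuous supportive variables are handled in parallel with the lesion counts. SAP 8.7.1.1 adjusts each lesion count for its own baseline.

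**The concern.** The tables report treatment p-values from a model whose covariate cannot be identified. There are two lesion counts, inflammatory and non-inflammatory, and neither is the baseline of redness, embarrassment or sadness. A programmer could defend three different models: a lesion count of unstated type (the footnotes), no covariate (8.1.4), or the item's own baseline (8.7.4 by analogy). The choice should be settled while the trial is blinded.

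The secondary question is what the endpoint is. The endpoint list uses the names of domains, the shells tabulate items, and the readable text gives no rule for combining items. SAP 8.7.5, by contrast, gives Acne-QoL a full scoring rule with handling of missing items.

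**Working it through.** The plan states no figure to reproduce here, so the check is mainly a comparison of texts.

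**Covariate**

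| Place | What it implies for a PRE-FACE item change |
|---|---|
| Footnotes a and c, both tables, all six pages | a baseline lesion count, type not stated |
| SAP 8.1.4 | no covariate beyond baseline lesion count for the primary lesion endpoint |
| SAP 8.7.4 read with 8.7.1.1 | the outcome's own baseline, by analogy |

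The wording was probably carried over. The same footnotes sit under the first two pages of Table 14.2.11.1, which hold only IGA rows.

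**Cost if the footnote were followed literally (illustration)**

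The assumptions, none of them from the documents, are as follows. Item scores have unit variance at both times. The baseline-to-visit correlation is r = 0.3 to 0.7. The lesion count's correlations with the visit score and with the baseline score differ by g = 0 to 0.2.

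- Change adjusted for the item's own baseline: variance = 1 − r².
- Change adjusted for lesion count: variance = 2(1 − r) − g². With g = 0 this is also the variance with no covariate.
- Reduction from using own baseline = 1 − (1 − r²) / [2(1 − r) − g²].

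| r | own baseline | lesion count, g = 0 | reduction | lesion count, g = 0.2 | reduction |
|---|---|---|---|---|---|
| 0.3 | 0.91 | 1.40 | 35.0% | 1.36 | 33.1% |
| 0.5 | 0.75 | 1.00 | 25.0% | 0.96 | 21.9% |
| 0.7 | 0.51 | 0.60 | 15.0% | 0.56 | 8.9% |

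Suppose instead that the lesion count has correlation 0.5 with the baseline item score and relates to the visit score only through it, so that g = 0.5(1 − r). The reduction is then 1 − 0.91/1.2775 = 28.8% at r = 0.3 and 1 − 0.51/0.5775 = 11.7% at r = 0.7, inside the same range. These formulas apply to the unranked analysis.

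**Items or domains**

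The shells hold 4 × 3 = 12 item rows for ASD and 3 × 3 = 9 for AID, 21 in all. One score per domain would give 2 × 3 = 6 comparisons, and the shells contain no such row. Table 14.2.9.1 and Listing 16.2.6.4 are also at item level. SAP 10 records a change to another supportive endpoint but says nothing about PRE-FACE.

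**Footnote b**

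Items 2 to 4 and 6 to 7 are not imputed, so they have no imputed datasets in which to assess skewness.

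**The case against.** The strongest reply is that nothing is really open. The shells are part of the SAP, which takes precedence over the protocol. They are titled as ASD and AID scores and list exactly items 1 to 4 and 5 to 7 at the three visits, which works as an operational definition, and the endpoint text speaks of scores in the plural. Where the authors wanted a composite, for Acne-QoL, they wrote a rule. The footnote is plainly boilerplate, and a sensible programmer would follow 8.7.4 and use the item's own baseline.

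Much of this stands for the secondary point. A reader might infer that two listed endpoints have no planned result at all, since none of the six domain comparisons is tabulated. The documents do not support that as a flat statement, because it holds only if scores means domain scores. The absence of a scoring rule is also judged without the PRE-FACE forms in protocol Appendices 2 and 3, which are figures not shown.

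For the covariate the reply is weaker. If own baseline is intended, footnotes a and c and 8.1.4 all misdescribe the model. It is true that 8.1.4 is already loosely worded, since the percent-change analyses in Table 14.2.8.1 also adjust for baseline lesion count. That is a reason to tidy 8.1.4, since it does not say which covariate applies.

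**Conclusion.** The covariate named for the PRE-FACE item analyses is wrong as written, and the SAP text does not clearly replace it. If it were followed literally, the loss would be precision only. A chance baseline imbalance in an item would be left less well corrected, but that is part of the lost precision, and reading it as bias would be a mistake under randomisation. The size, roughly 10% to 35% of variance, rests wholly on assumed correlations. If the analysis is programmed with own baseline, nothing is lost and only the description is wrong.

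The ASD and AID wording is ambiguous, and the endpoint text and the shells should be made to agree. A reader might also see 21 item tests as a threat to type I error control. They are supportive and lie outside the gated sequence, so they do not affect it. Co-primary and gated secondary inference is unaffected, including the responder analyses of items 1 and 5, which use logistic regression without a baseline covariate. The point is minor.

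**What to change.** Before unblinding:

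1. In footnotes a and c of Tables 14.2.12.1 and 14.2.13.1, name the respective baseline PRE-FACE score as the covariate. Amend SAP 8.1.4 and 8.7.4 to match.
2. Settle the endpoint in one of two ways. Either reword the two lines in SAP 7.1.3 to say that item scores are the endpoints and record this in SAP 10, or define the ASD and AID scores by the instrument's own rule and add domain rows at Weeks 2, 4 and 8. The second route needs a missing-item rule and one stated missing-data approach for all items in a domain, because at present only items 1 and 5 are imputed.
3. Limit footnote b to the imputed item in each table, item 1 or item 5.

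The item rows already planned can stay. The cost is a sentence or two in each of 8.1.4 and 8.7.4, three footnotes in two shells, and then either two reworded endpoint lines with one entry in SAP 10 or a short scoring paragraph with six added rows. No new data are needed, since the protocol flow chart has PRE-FACE completed at Baseline and every later visit. New random seeds would be needed only if further items were imputed.
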